6.1 Statistical Model

The PO model can be written in terms of the covariates X and an outcome variable Y , where probabilities of outcome value y or greater $\Pr(Y \geq y|X) = \text{expit}(\alpha_y + X\beta)$ where α_y is the intercept for outcome value y and expit is the logistic (inverse logit) transformation and the columns of matrix X contain coded baseline covariates and the active/placebo treatment indicator. β represents the log odds ratio (OR) associated with the effects of covariates and group assignment. Specifically, the group assignment odds ratio represents the relative effect of treatment versus placebo on the odds $\Pr(Y \geq y|X)/(1 - \Pr(Y \geq y|X))$, for any value y .

A flat prior distribution will be used for all PO model parameters. This ensures that the estimate of the primary estimand will be free of influence from an informative prior, and the Bayesian maximum *a posteriori* estimate will be identical to the maximum likelihood estimate (see Appendix: Cumulative Logit Model). The posterior distribution for the log odds ratio will be approximated using the Laplace method.⁸ Use of a flat prior ensures the Laplace-approximated posterior distribution is identical to the asymptotic sampling distribution of the maximum likelihood estimate; in both cases a normal distribution centered at the estimate with variance-covariance equal to the negative inverse Hessian of the log likelihood function (inverse observed Fisher information; see Appendix: Laplace Approximation). All statistical inferences about the odds ratio will be made using this method. Statistical uncertainty about supplementary estimands (e.g., treatment difference in the median of the primary outcome) will be quantified using the delta method.⁹ Given the investigational nature of the agents tested by this platform, there is insufficient information upon which to justify a more informative prior. The flat prior approach ensures that Bayesian inferences regarding the efficacy of study agents are based exclusively on the data collected in the ACTIV 4 Host Tissue platform.

6.3 Planned Interim and Final Analyses, Early Stopping, and Type-I Error Control

Two planned interim analyses will occur separately for each study arm when the number of participants with complete 28-day follow-up (or were deceased, withdrawn, or lost-to-follow-up by day 28) reaches 33% and 67% of maximum enrollment for that arm. Interim analyses will be executed by unblinded personnel only. Participant records that inform the primary outcome must undergo monitoring prior to interim (and final) analysis. At each interim analysis, a study arm may be stopped early if there is evidence for inferiority/harm. Enrollment in the trial will be stopped early if the posterior probability for inferiority/harm exceeds 0.95.

Final analysis will occur once enrollment, follow-up, and the required monitoring are completed. Should additional data be collected after enrollment is halted at an interim analysis, the final analysis will incorporate this additional data. If the trial was stopped early at an interim analysis due to evidence of inferiority/harm, a conclusion of inferiority/harm will be indicated if the posterior probability for inferiority/harm remains greater than 0.95 at the final analysis. If the trial was not stopped early at an interim analysis due to evidence of inferiority/harm, efficacy will be indicated if the posterior probability for efficacy regarding the primary outcome exceeds a threshold as follows: For studies under this master protocol, the efficacy threshold was selected using statistical simulation to ensure a type-I error probability of 2.5% for each study arm. In all other scenarios, the trial is inconclusive.

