### 8.1 Statistical and Analytical Plans

There will be a formal Statistical Analysis Plan (SAP). This SAP will provide detailed descriptions of all primary, secondary, and sensitivity analyses, all interim and final decision thresholds, and all required documentation to ensure the reproducibility of statistical analyses. The SAP will be finalized prior to the first interim analysis for the platform, and arm-specific SAP amendments (if required) will occur before the first interim analysis involving that arm. The finalized SAP will take precedence and override the statistical considerations described in this section of the master protocol (i.e., Statistical Considerations).

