Based on these data and effect size scenarios, a series of statistical simulations were implemented to examine the operating characteristics of the statistical study design described above, including the plan for randomization, interim analysis, and final assessments of efficacy using the odds ratio. In each simulation, participant age group, sex, and baseline WHO COVID severity score were randomly sampled with replacement from the values observed, and their effects on the primary outcome were simulated to match the estimated effects of age, sex, and WHO score on the primary outcome among the first 100 participants and loss-to-follow-up, partially observed oxygen free days were simulated to match the observed frequency of partially observed outcomes, which occurred in 12% of the first 100 participants. To encode attrition, a subset of the simulated study participants was selected at random, each with probability 0.12. The primary outcome for each selected participant was encoded as partially observed by assuming that oxygen free days may have taken any value between -1 and a randomly sampled value ranging from the simulated oxygen free days to 28. For example, if the simulated oxygen free days is 10, then a value between 10 and 28 is sampled uniformly at random and this value is treated at the upper limit for the partially observed oxygen free days. This pattern of partially observed oxygen free days closely resembles the patterns observed among the first 100 participants. All simulation analyses, including those

associated with interim and final assessment of efficacy and inferiority were implemented using the methods described above for the analysis of the primary outcome.

Simulation under the null hypothesis was used to select the efficacy threshold for the final analysis of the primary outcome. The efficacy threshold was selected to ensure no more than 2.5% type-I error. In this simulation, 10000 replicates were used to ensure ~0.31% simulation margin of error in estimating the type-I error rate. The efficacy threshold was identified as 0.9760. The efficacy and inferiority/harm thresholds will be applied as follows:

Analysis	Rule	Result
Final analysis (only)	Efficacy probability > 0.976	Conclude efficacy
Each interim and final analysis	Inferiority/harm probability > 0.950	Stop and conclude inferiority/harm

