Simulation under the null hypothesis was used to select the efficacy threshold for the final analysis. The efficacy threshold was selected to ensure no more than 2.5% type-I error. In this simulation, 10000 replicates were used to ensure ~0.31% simulation margin of error in estimating the type-I error rate. The efficacy threshold was identified as 0.976. A final analysis will occur once enrollment, follow-up, and the required monitoring are completed for all participants. Should additional data be collected after enrollment is halted at an interim analysis, the final analysis will incorporate this additional data. If enrollment was halted at an interim analysis due to evidence of inferiority/harm, a conclusion of inferiority/harm will be indicated if the posterior probability for inferiority/harm remains greater than 0.95 at the final analysis. If the trial was not stopped early at an interim analysis due to evidence of inferiority/harm, efficacy will be indicated if the posterior probability for efficacy regarding the primary outcome exceeds 0.976 at the final analysis. If neither condition is met for a conclusion of efficacy or inferiority/harm at the final analysis, the trial is inconclusive. The efficacy and inferiority/harm thresholds will be applied as described in the table below.

Analysis	Condition	Action
Interim analysis	Inferiority/harm probability > 0.950	Halt enrollment
Final analysis	Inferiority/harm probability \leq 0.950 at all interim analyses and efficacy probability > 0.976	Conclude efficacy
Final analysis	Inferiority/harm probability > 0.950	Conclude inferiority/harm

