Using the selected efficacy and inferiority/harm thresholds, the results of 10000 simulations under the null hypothesis, and 1000 simulations per inferiority/efficacy scenario are summarized in the table below. In these simulations, the type-I error probability was 2.47%. The frequency of stopping early for inferiority under the null was 8.6% (5.3% at the first interim analysis, and 3.2% at the second interim analysis). A *maximum sample size of 600 participants per trial provides greater than 85% power to detect an odds ratio of 1.65, corresponding to a 3.1-day difference in mean OFDs, and a 7.8 percentage point reduction in 28-day mortality*. Differences larger than 2 ventilator-free days on average have been considered clinically important in prior trials.²⁻⁴ Thus, the minimum detectable effect with 85% power (MDE85) is an odds ratio of 1.65. The frequency of stopping early for inferiority when there was an effect larger than OR=1.40 was <1%. When the simulated treatment was inferior/harmful relative to placebo, at OR=0.67, a conclusion of inferiority/harm occurred in 83.3% of simulated trials (39.1% at the first interim, 27.9% at the second interim, and 16.3% at the final analysis), and the average half-sample size was 193.9 per arm.

	Null	Inferiority		Superiority						
	1.00	0.67	0.80	1.40	1.45	1.50	1.55	1.60	1.65	1.70
OFDs / Odds Ratio	1.00	0.67	0.80	1.40	1.45	1.50	1.55	1.60	1.65	1.70
Pr(Efficacy)	0.025	0.000	0.001	0.552	0.631	0.705	0.782	0.826	0.856	0.893

OFDs / Odds Ratio	Null	Inferiority		Superiority						
	1.00	0.67	0.80	1.40	1.45	1.50	1.55	1.60	1.65	1.70
Pr(Inferiority)	0.108	0.833	0.508	0.003	0.002	0.001	0.000	0.000	0.001	0.000
Pr(Inconclusive)	0.867	0.167	0.491	0.445	0.366	0.294	0.218	0.173	0.143	0.107
Average(N/2)	286.1	193.9	242.0	299.4	299.8	299.8	300.0	300.0	299.8	300.0

In order to characterize the effect of uncertainty in the distribution of the OFD outcome on the type-I error probability, simulations under the null hypothesis were twice repeated assuming a “mild” and “severe” distribution for the OFD outcome. The mild and severe distributions were selected such that the unadjusted mortality rate ranged $\pm 3\%$ relative to the initial simulation. The results of 1000 simulations in each of the mild placebo and severe placebo scenarios are summarized in the table below. In these simulations, the type-I error probability was 2.5% and 2.3%.

	Severe	Mild
	OR = 1.00	OR = 1.00
Mortality rate	0.266	0.206
Pr(Efficacy)	0.023	0.025

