7.2 Analysis of Safety, Adherence, and Retention Outcomes for DSMB Review

Monitoring and reporting of safety events will be conducted continuously as described in the Data and Safety Monitoring Plan. Records will undergo monitoring for a two-week period (at minimum) prior to interim analysis for inferiority or futility. However, all records, regardless of monitoring status, will be used in enrollment, demographic, and safety summaries for DSMB safety reporting. Agent-specific safety and toxicity endpoints (if any) are detailed in that therapy’s appendix. The frequencies of PSESEs, adverse events, mortality, and other safety endpoints will be reported. Screening, enrollment, withdrawal, loss-to-follow-up, mortality, study completion, hospitalization status and discharge location will be summarized in a similar manner. All safety-related protocol violations will be listed in the DSMB report. Receipt of planned therapy and adverse events will be recorded on case report forms and monitored continuously. Study drug stoppages and adverse events will be summarized and reported to the DSMB.

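### The SAP text allows a harm conclusion only after an interim halt, but the SAP table does not; under the text, the stated 83.3% at an odds ratio of 0.67 is at most 67.0%

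*SAP*

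**What the plan says.** SAP section 6.3 takes the two cases in turn. If the trial was stopped early at an interim for harm, "a conclusion of inferiority/harm will be indicated if the posterior probability for inferiority/harm remains greater than 0.95 at the final analysis". If it was not stopped early, the only conclusion offered is efficacy. The section then closes the list: "In all other scenarios, the trial is inconclusive".

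The text of SAP section 6.6 repeats the rule for halted trials and calls a trial inconclusive when neither condition is met. It then says "The efficacy and inferiority/harm thresholds will be applied as described in the table below". That table has a final-analysis row that concludes harm whenever the harm probability exceeds 0.950. The row does not require an earlier halt, although the efficacy row does carry an explicit condition on the interims.

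On data arriving after a halt, section 6.6 says "Should additional data be collected after enrollment is halted at an interim analysis, the final analysis will incorporate this additional data". On interim timing, section 6.3 counts participants with complete 28-day follow-up, and section 7.2 adds "Records will undergo monitoring for a two-week period (at minimum) prior to interim analysis for inferiority or futility".

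At an odds ratio of 0.67, section 6.6 reports a harm conclusion in 83.3% of simulated trials, split as "39.1% at the first interim, 27.9% at the second interim, and 16.3% at the final analysis".

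The table in protocol section 8.6.5 words the rule a third way. At any interim or the final analysis, a crossing means "Stop and conclude inferiority/harm". Protocol section 8.1 settles that difference: "The finalized SAP will take precedence and override the statistical considerations described in this section of the master protocol".

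**The concern.** Take a trial that is never halted, enrols all 600 participants and ends with a harm probability above 0.95. Section 6.3 calls it inconclusive; the section 6.6 table calls it harmful. Both rules are in the SAP, so the SAP's precedence over the protocol does not decide between them. If this is left open, the label could be chosen after the result is known, in the case that matters most for safety.

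A second gap concerns the same figures. Patients keep enrolling while an interim waits for follow-up and record monitoring, because no enrolment pause is stated. The SAP puts their data into a final re-test, and a halted trial keeps its harm conclusion only if it passes. If the simulation left this step out, the stated harm probabilities and average sample sizes do not describe the procedure as written.

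**Working it through.** **Inputs.** All are from SAP sections 6.3 and 6.6: maximum 300 per group; interims at 33% and 67% (100 and 200 per group); harm threshold 0.95 and efficacy threshold 0.976; at odds ratio (OR) 0.67, harm split 39.1% / 27.9% / 16.3% and average N/2 of 193.9; under the null, interim halts 5.3% and 3.2% (stated total 8.6%), harm 10.8% and average N/2 of 286.1; at OR 0.80, harm 50.8% and average N/2 of 242.0.

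**1. Reproduce the stated figure.** 39.1 + 27.9 + 16.3 = 83.3%. This is the table rule, because the last 16.3% were never halted.

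**2. Apply the text.** Only halted trials can conclude harm.
- OR 0.67: harm at most 39.1 + 27.9 = 67.0%; inconclusive at least 100 − 67.0 = 33.0%, against 100 − 83.3 = 16.7%.
- Null: harm at most 8.6%, against 10.8%.

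These are upper limits because a halted trial must also pass the final re-test.

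**3. Was overrun simulated?** If stopping occurs at exactly 100, 200 or 300 per group:
- OR 0.67: 0.391×100 + 0.279×200 + 0.330×300 = 193.9 (stated 193.9).
- Null: 0.053×100 + 0.032×200 + 0.915×300 = 286.2 (stated 286.1; rounding).

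No patients were added after a halt.

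**4. OR 0.80.** The SAP gives no split by analysis. With halt shares p1 and p2, 300 − 200·p1 − 100·p2 = 242.0, so 2·p1 + p2 = 0.58. With p1 + p2 ≤ 0.508, interim halts lie between 29.0% (p2 = 0) and 50.8%. A normal approximation puts p1 at 0.194 to 0.201, giving p1 + p2 of about 38%. The stated harm probability is 50.8%.

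**5. Size of the overrun effect.** No per-arm accrual rate is given, so it is assumed and ranged.
- Overrun = monthly accrual × days / 30.4. The 42-day delay is 28 days of follow-up plus the two-week minimum for monitoring; 60 days is an assumed longer delay.
- Model: normal approximation with independent increments, 1,000,000 paths, looks at 1/3, 2/3 and 1, harm bound z < −1.645, re-test at interim size plus overrun.
- Standard error of the log OR at full size, from the stated powers: SE = ln(OR)/(z₀.₉₇₆ + z_power). OR 1.40 at 55.2% power gives 0.3365/(1.977 + 0.131) = 0.160; OR 1.70 at 89.3% gives 0.5306/(1.977 + 1.243) = 0.165.
- Check without overrun: OR 0.67 gives 82.7–84.3% (stated 83.3%); OR 0.80 gives 47.1–48.5% (stated 50.8%); null gives 10.1% (stated 10.8%). The approximation is close at 0.67 and runs about 1 to 4 points low elsewhere.
- Average N/2 at OR 0.67 = 193.9 + 0.670 × overrun/2.

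| Overrun (patients) | Assumed accrual, delay | OR 0.67 harm, table | OR 0.67 harm, text | OR 0.67 average N/2 | Null harm, table | Null harm, text |
|---|---|---|---|---|---|---|
| 14 | 10/month, 42 days | 78.0–79.8% | 62.6–64.8% | 198.6 | 8.5% | 6.4% |
| 28 | 20/month, 42 days | 76.8–78.7% | 61.5–63.6% | 203.3 | 7.8% | 5.7% |
| 55 | 40/month, 42 days | 76.0–77.9% | 60.6–63.0% | 212.3 | 7.2% | 5.1% |
| 110 | 80/month, 42 days | 75.8–77.8% | 60.5–62.8% | 230.8 | 6.3% | 4.2% |
| 160 | 80/month, 60 days (158) | 76.2–78.4% | 60.9–63.4% | 247.5 | 5.8% | 3.7% |

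**The case against.** The best defence is that the SAP already shows which rule it means. Section 6.6 says the table governs how the thresholds are applied, the table's harm row has no halt condition, the simulation counts harm conclusions at the final analysis, and the protocol table also allows them there. On that reading the 83.3% is correct for the rule that was simulated, and 67.0% describes a rule nobody intended. The section 6.6 text never says that harm can be concluded only after a halt, so the one flat contradiction is the closing sentence of section 6.3. The consequence is also narrow: enrolment is over, the estimate and credible interval are reported either way, and no efficacy decision changes.

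Much of this stands. It is good evidence that the table is the intended rule, and it limits the weight of the point. It does not remove the conflict. Section 6.3 excludes the table's outcome without referring to the table, and the neither-condition sentence in section 6.6 most naturally refers to the two conditions just stated, one of which requires a halt.

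It can also be said that the overrun is a separate matter resting on assumed accrual, and that 60 days has no source. That is fair about its exact size. The only duration given, 15 months for the platform (protocol section 2), would imply roughly 600/15 = 40 patients a month, which is inside the assumed range. That no overrun was simulated follows from the SAP's own averages and needs no assumption.

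**Conclusion.** The concern holds. The SAP gives two different conclusions for a full-size trial with a harm probability above 0.95, and its operating characteristics match only the table. At OR 0.67 this affects 16.3% of simulated trials, about one in six. The limits of 67.0% (OR 0.67) and 8.6% (null) under the text come directly from the SAP's figures.

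Under the table, 83.3% stands only if there is no overrun. With 14 to 160 overrun patients, harm at OR 0.67 is about 76–80% under the table or 60–65% under the text, and average N/2 is about 199 to 248. Under the null, harm is about 5.8–8.5% or 3.7–6.4%. These ranges rest on the assumed accrual and delay and on a normal approximation that runs slightly low away from OR 0.67.

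The conflict does not affect efficacy type-I error control or the 0.976 threshold. It concerns the formal conclusion and the published operating characteristics, so it should be fixed but does not threaten the primary efficacy test.

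**What to change.** Amend the text of SAP sections 6.3 and 6.6 to match the SAP table, for example: *At the final analysis, conclude inferiority/harm if its probability exceeds 0.95, whether or not enrolment was halted; conclude efficacy if enrolment was not halted for harm and the efficacy probability exceeds 0.976; otherwise the trial is inconclusive.*

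For consistency, align the protocol section 8.6.5 table, although the SAP overrides it: an interim crossing halts enrolment, and the conclusion is drawn at the final analysis.

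Rerun the simulation with overrun and the final re-test, over a stated range of accrual and delay. Restate the harm probabilities of 83.3%, 50.8% and 10.8% and the average sample sizes.

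The cost is two SAP sentences, one protocol table row and one simulation rerun. The restated harm probabilities will be somewhat lower and the average sample sizes higher.

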6.4 Supplementary Efficacy Estimands

The PO model is attractive for the analysis of ordinal and quantitative response variables, such as the primary outcome, because they directly model the cumulative distribution function from which the mean, median, other percentiles, and cumulative probabilities of the primary outcome, stratified by treatment group, are easily derived.¹² In addition to the odds ratio, the effects of treatment versus placebo will be quantified using the difference in mean, difference in median, and differences in clinically relevant proportions associated with the primary outcome: mortality at day 28: $\Pr(Y = -1|X)$, and oxygen requirement every day until day 28: $\Pr(Y = 0|X)$, adjusted to the modal value for each covariate. These important and clinically meaningful supplementary estimands will be used to describe and communicate the treatment effect. The posterior distribution for each of the supplementary estimands is readily computed using standard Bayesian methods.

6.5 Sensitivity and Supplementary Analyses

Sensitivity and supplemental analyses will be implemented at the final analysis.

Most regression methods, including proportional odds logistic regression, Cox proportional hazards regression, and linear (mean) regression, assume that the effects of the independent variables are consistent across the outcome distribution. Violation of this assumption is a complex situation that implies a heterogeneous treatment effect. For example, the active drug group might experience more frequent extreme outcomes (death and 28 oxygen-free days) versus the placebo group. In this type of situation, much like differential treatment effects observed across participant strata such as sex, no single summary fully describes the treatment effect, and the differential treatment effects must be carefully examined and interpreted in their totality. The *proportional odds assumption* of the PO model specifies that the effect of treatment on the odds that $Y \geq 3$ (measured as an odds ratio versus placebo) is the same relative effect as for $Y \geq 4$. However, even when the PO assumption is strongly violated, the estimated OR remains a simple function of the Wilcoxon-Mann-Whitney U-statistic, namely the probability that a randomly chosen patient on treatment B has a higher response than a randomly chosen

patient on treatment A,¹³ the *probability index* or *concordance probability*. In addition, under the null hypothesis, the PO assumption is always satisfied. Thus, statistical testing based on the odds ratio, as estimated using the PO model, has the specified type-I error rate and provides a reasonable global assessment of treatment effectiveness, regardless of violations of the proportional odds assumption. However, derived quantities such as the difference in means may be more sensitive to violations of the PO assumption. Deviations from proportional odds will be examined by separately estimating the odds ratio for each possible dichotomization (that preserves ordering) of the primary outcome (e.g., alive versus dead at day 28, alive and oxygen free for at least 10 days at day 28 versus alive and oxygen free for fewer than 10 days or dead at day 28, etc.), in a planned sensitivity analysis. These analyses will be implemented using the logistic regression method described below (see *Logistic Regression (LogR)*). No hypothesis testing will be implemented regarding the PO assumption. This sensitivity analysis serves the following two purposes: 1) to assess for evidence of violation of the proportional odds assumption and 2) to estimate the differential treatment effects (with 95% credible interval) when the proportional odds assumption is relaxed. The latter provides the information needed to interpret the treatment effects should there be evidence of violation of the proportional odds assumption. In addition, as a key secondary outcome, we will quantify the effect of treatment on 28-day mortality, which directly addresses the possibility that treatment affects 28-day mortality differently than cumulative oxygen use within the first 28 days. This analysis enables us to detect non-proportional effects of the treatment on the two major components of the primary outcome, mortality, and oxygen-free days.

As a supplementary analysis to inform decision-making in the event there is evidence of violation of the PO assumption, we will implement an alternative primary outcome using a partial proportional odds (PPO) model¹⁴, where the effect of the study intervention and each covariate will be allowed to vary across all possible order-preserving dichotomizations of the primary outcome. These covariate effects will be “unconstrained.” However, to ensure estimability of this model, and to shrink toward the PO model, a weakly informative prior will be assigned to shrink each dichotomization effect toward the common effect. The log odds ratio for each dichotomization will have a normal prior distribution centered at the common log odds ratio with standard deviation 0.354, which assigns 95% prior probability that each dichotomization odds ratio falls within a factor of 0.5 and 2.0 of the common odds ratio. The estimated common odds ratio from the PPO model will be evaluated in a manner similar to the common odds ratio in the primary analysis using the PO model. Specifically, we will report the estimated common odds ratio with 95% credible interval and the posterior probability for efficacy. Due to limitations of existing software to implement the PPO model, partially observed values of the primary outcome will be treated as missing.

Analysis of partially observed or missing outcome data requires assumptions regarding the mechanism by which censoring and missing values arise. The likelihood method described above, and other similar methods such as multiple imputation assume that missing values occur at random (i.e., missing at random or MAR). However, because censored and missing values cannot be observed, assumptions about the missingness mechanism are not verifiable. In order to assess the sensitivity of study findings to violations of this assumption, we will conduct additional sensitivity analyses by reproducing the primary analysis under alternative assumptions regarding the mechanism for missing values. Specifically, we will perform sensitivity analyses that vary assumptions about the missing outcomes on the two treatment arms separately. These analyses will consider the following two scenarios: 1 “missing favors inefficacy”) each partially observed primary outcome in the placebo group will be assumed to have taken the highest/best possible value, whereas each partially observed primary outcome in the intervention group will be assumed to have taken the lowest/worst possible value, and 2

“missing favors efficacy”) each partially observed primary outcome in the placebo group will be assumed to have taken the lowest/worst possible value, whereas each partially observed primary outcome in the intervention group will be assumed to have taken the highest/best possible value. These analyses will be implemented using the primary analysis methodology, including an assessment of hypothesis testing outcomes. For any trial under this platform, if there is a conclusion of efficacy at the final analysis, and the conclusion would have been different under the “missing favors inefficacy” scenario, then an additional tipping-point analysis will be implemented to estimate the association between the degree to which missing values must favor inefficacy versus the probability the trial would have failed to conclude efficacy. In these analyses, the partially observed outcomes will be randomly imputed under the assumption that partially observed outcomes favor the inefficacy conclusion by a specified amount. The degree to which the partially observed outcomes favor inefficacy will be encoded using an odds ratio that adjusts the outcome probabilities conditional on the participant covariates, using the maximum a posteriori (MAP) estimate at the final analysis. These probabilities will then be used to randomly sample the outcome for imputation purposes. For partially observed outcomes that exclude some levels of the outcome, the sampling probabilities for the excluded levels will be set to zero and the remaining probabilities normalized to sum to one. After sampling the outcome for all partially observed outcomes, the primary analysis will then be implemented using the imputed outcome data and the study conclusion recorded. This process will be repeated 1000 times and the probability of a trial conclusion other than efficacy will be calculated using a Monte-Carlo estimate. This process will again be repeated for a range of odds ratios encoding the degree to which the partially observed outcomes favor inefficacy. Specifically, this will be guided by two parameters: α_0 and α_1 , where α_0 is the log odds ratio of more oxygen free days comparing partially missing versus non-missing placebo arm participants and α_1 is the log odds ratio of a higher score comparing partially missing versus non-missing active arm participants. We will vary both parameters across the tipping point analysis within in the following range (-0.5, -0.25, 0.25, 0.5) (i.e., 16 total scenarios). We chose this range of parameters because together they induce a treatment effect in the partially observed participants that ranges from reasonably pessimistic to reasonably optimistic. If β is the observed log odds ratio (active versus control) in the analysis, then the treatment effect in the partially observed participants would range from $\beta-1$ to $\beta+1$. This range (2 on the log odds ratio scale) is four times the anticipated treatment effect for which the study is powered (i.e., to detect a log odds ratio equal to 0.5, or an odds ratio equal to 1.65). The results of this sensitivity analysis will be summarized graphically.

Co-enrollment in other studies testing COVID-19 therapeutics may occur. Co-enrollment may affect the treatment effect estimates if there is effect modification associated with co-enrollment. We expect co-enrollment to occur in fewer than 5% of patients enrolled in the trial. However, because the decision to co-enroll is not affected by the treatment assignment in ACTIV 4 Host Tissue, co-enrollment will not favor any particular treatment. In addition, due to its rarity, we expect co-enrollment to have little impact on the estimated treatment effects, even when there is effect modification.

Differential treatment effect, also referred to as heterogeneity of treatment effect, refers to differences in efficacy as a function of pre-existing patient characteristics such as baseline variables. This is often assessed by forming subgroups or using an interaction analysis. Supplemental interaction analyses will be implemented to examine the potential for differential treatment effect. Differential treatment effect will be examined in strata defined by (but not limited to) respiratory support category at enrollment, status of co-enrollment in an open label clinical trial of antiplatelet agents (ACTIV 4a), age category, SARS-CoV-2 vaccination status, passive immunity status, co-enrollment in other studies, and concomitant use of study drug and

other medications during the study drug administration period. These analyses will be implemented using a modified version of the primary analysis method, where the treatment effect will be estimated separately for each level of the stratification variable. Stratum-specific treatment effect estimates will be presented with 95% Bayesian confidence interval. No formal hypothesis testing will be implemented for these analyses. Studies under this master protocol will be sized only for assessing efficacy using the primary analysis. Thus, there may be inadequate power to examine differential treatment.

